**Table 2: Visit Window for Safety Analyses**

Timepoint	Target Visit Date	Visit window (in study days)
Visit 1 (baseline)	1	-45 to 1
Visit 2 (week 20)	140	71 to 210
Visit 3 (week 40)	280	>=211

#### 5.3. Missing Data Handling

Unless specified, observed data will be used for all analyses. Missing data will not be imputed.

#### **5.4. Interim Analysis**

No interim analysis will be conducted for this study.

#### **5.5. Multicenter, Multiplicity control**

This is a multicenter study with all muscle biopsies performed at one center. No multicenter analysis will be conducted for this study.

There is only one primary efficacy endpoint, and one secondary efficacy endpoint for this study. The secondary efficacy endpoint will be analyzed if the primary efficacy endpoint is statistically significant at 0.05 significance level. All other endpoints and analyses are supportive. Therefore, no multiplicity adjustment will be conducted for this study.

#### **5.6. COVID-19 Related Considerations**

Due to the Coronavirus Disease of 2019 (COVID-19) pandemic, 8 subjects will have Visit 3 (Week 40 visit) later than planned due to closure of the study site to study procedures. These subjects will receive continued therapy with ataluren until final study biopsies can be obtained. Since many subjects will have their Week 40 biopsy performed much later than after 40 weeks of ataluren treatment therapy, a sensitivity analysis will be conducted to include the Week 40 biopsy study day as a covariate in the analysis model. This sensitivity analysis will be performed for both the primary and secondary efficacy endpoints as detailed in Section 7.1.3 (Sensitivity Analyses) for the primary efficacy endpoint and in Section 7.2.2 (Sensitivity Analyses) for the secondary efficacy endpoint.

### **6. SUBJECT DATA**

#### **6.1. Subject Disposition and Study Populations**

The number of subjects in each analysis population will be summarized using frequency count.

The number of subjects who completed or discontinued from the study and the reasons of discontinuation will be summarized based on both the ITT and the safety populations if they are different.

#### **6.2. Treatment Exposure**

The extent of exposure (duration of exposure) to study drug will be summarized using descriptive statistics and tabulated with frequency count by categories. Duration of exposure of study drug will be defined as the number of days between the date the subject received the first dose of study drug during treatment period and the date the subject received the last dose of study drug during treatment period, inclusive. Duration of exposure will be categories as <266 days, 266 to 295 days and >295 days. Treatment exposure will be summarized based on both the ITT and safety populations if they are different.

### 6.3. Study Drug Compliance

Treatment compliance (in %) is defined as follows:

$$\frac{100 \times (\text{total number of sachets dispensed} - \text{total number of sachets returned or lost})}{\text{number of sachets expected to be taken}}$$

Treatment compliance will be summarized using descriptive statistics based on the safety population. Treatment compliance will also be summarized using the categories <80%, ≥80% to ≤100%, >100% to ≤120%, and >120%.

### 6.4. Demographic and Baseline Characteristics

Unless otherwise specified, baseline measurement is the last observed measurement prior to the first dose of study drug for a given assessment.

Continuous demographic and baseline variables including age, age at onset of phenotypic evidence, age at first observation of difficulty with ambulation, height, weight, and body mass index will be summarized using descriptive statistics. Categorical variables including ethnicity group, race, and type of corticosteroid use will be tabulated using frequency count. Demographic and baseline characteristics will be summarized based on both the ITT and safety populations if they are different.

Genotype information including the location of nonsense point mutation (exon number) and the stop codon type will be tabulated using frequency count and displayed in subject listings.

### 6.5. Concomitant Medications and Non-Drug Treatments

Medications and non-drug treatments will be coded using the World Health Organization Drug Dictionary, version September 1, 2020. Prior medications and prior non-drug treatments are defined as those taken any time prior to first dose of study drug. Concomitant medications and non-drug treatments are defined as those taken any time on or after first dose of study drug.

The number and percentage of subjects who take prior and concomitant medications will be summarized using the safety population by Anatomical Therapeutic Chemical class, and WHO DD preferred term (PT) for safety populations. If a subject takes the same medications for the same class level or drug name, the subject will be counted only once for that class level or drug name.

### 6.6. Medical History

Medical history other than the history of dystrophinopathy will be coded using the Medical Dictionary for Regulatory Affairs (MedDRA), version 23.1. The number and percent of subjects with medical history will be summarized by System Organ Class (SOC) and PT based on safety population.

## 7. EFFICACY EVALUATION

The primary efficacy assessment for this study is the dystrophin levels obtained from muscle biopsies. Muscle biopsies of [REDACTED] muscles will be performed using an established core biopsy procedure at baseline and after 40 weeks of ataluren therapy. If the [REDACTED] muscle is considered by the investigator to be too small for a biopsy sample (or the obtained sample is considered not evaluable for analysis), the [REDACTED] muscle may be used. [REDACTED] cores of muscles will be taken from each location and multiple samples will be prepared from each muscle cores. Dystrophin levels will be measured from each sample by both ECL and IHC. The dystrophin levels measured by ECL will be considered as the primary efficacy endpoint. The dystrophin levels measured by IHC will be considered as the secondary efficacy endpoint.

### 7.1. Primary Efficacy Analyses

#### 7.1.1. Primary Analysis

The primary efficacy endpoint is the percent change from baseline in dystrophin levels (final concentration) following 40 weeks of ataluren therapy, as measured by ECL. The final concentration is calculated by dividing a sample's dystrophin concentration by its total protein concentration. In addition, the percentage of the predicted levels (% normal) will also be calculated as dystrophin levels normalized to dystrophin concentration of the control population ([Syneos Health Report No. 14597.051619.A](#)):

$$\% \text{ normal (in \%)} = 100 * \text{final concentration} / 33.8$$

Within each muscle location, the best, median, and the average of the dystrophin levels and the corresponding % normal values of the muscle cores will be summarized using descriptive statistics for each subject. In case any measured dystrophin concentrations are below the lower limit of quantification (LLOQ), the dystrophin concentrations will be set at 0.5\*LLOQ in the final concentration calculation for the statistical analysis.

The null hypothesis of the primary analysis is that the percent change from baseline in dystrophin levels following 40 weeks of ataluren therapy as measured by ECL is zero with the alternative hypothesis being that the change is greater than zero. To evaluate this hypothesis, a one-sided test at the 5% significance level will be employed.

The percent change from baseline at Week 40 in dystrophin levels measured by ECL will be analyzed using the mixed effect model repeated measurement (MMRM) analysis with factors of muscle locations, visits (baseline and Week 40) as fixed effects, and subjects as a random effect, based on ITT population. An unstructured covariance matrix will be used, and if the model fails to converge, then a compound symmetry matrix will be used. Since dystrophin level is known to be non-normally distributed, a log-transformation will be used in the analysis. The best dystrophin levels across all muscles are considered the primary analysis. A sample SAS code of the MMRM model is provided as follows:

```
proc mixed data = dataset;  
  
class subjid visit mlocation; /*mlocation is muscle location*/  
  
model lnaval = visit mlocation; /*lnaval is log-transformed dystrophin level*/  
  
random subjid;  
  
repeated visit / type = un;  
  
estimate "Week 40 change from baseline" visit -1 1;  
  
run;
```

As supportive analyses, the average and median dystrophin levels across all muscles, and the subgroup analyses of the best, median, and mean dystrophin levels within each muscle location will be considered. In addition, the two-sided 90% confidence interval of percent change from baseline in dystrophin levels at Week 40 and the ratio (%) of dystrophin level at Week 40 versus baseline will also be provided.

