## **8.4 Statistical Analyses**

### **8.4.1 General approach**

### **8.4.2 Analysis of primary efficacy endpoint**

The primary endpoint will be log transformed and analyzed in a mixed model of repeated measures with week/treatment as a fixed effect and subject as a random effect. Two-sided 90% CI for the ratio (%) of dystrophin level at Week 40 versus baseline will be constructed. The dystrophin level will be summarized by muscle biopsy locations using descriptive statistics.

Baseline dystrophin levels in this patient population is expected to be close to zero, in case any measured dystrophin levels are below the lower limit of quantification (LOQ), the levels will be set at  $0.5 \times \text{LOQ}$  for the statistical analysis. Subjects with baseline dystrophin levels [REDACTED] of the predicted levels will be excluded from the primary analysis to minimize the potential bias in the assessment of change in dystrophin levels.

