### 3.3. Sample Size Determination

Approximately, 15 to 20 ataluren-naïve male subjects, aged  $\geq 2$  and  $< 8$  years of age is planned to be enrolled in this study. Limited information is available about the magnitude and intra-subject variability of the change in dystrophin levels, as measured by an immunoassay such as ECL following 40 weeks ataluren therapy in this patient population. Assuming a baseline dystrophin level of 0.2% of control levels (as per previous dystrophin replacement therapy [Center for Drug Evaluation and research Application number: 206488Orig1s000 Eteplirsen Summary Review]), Table 1 shows the number of subjects needed to achieve an 85% power to detect an increase from baseline in dystrophin of 0.04%, 0.06% and 0.08%, for intra-subject coefficients of variability ranging from 20% to 35%, using a one-sided test at alpha 5%. As an example, if the increase from baseline is 0.08% and the intra-subject coefficient is 30%, 13 evaluable subjects would be required to have a power of 85% to detect this increase.

**Table 1: Summary of number of subjects required to achieve 85% power to detect increase in dystrophin levels from baseline**

Increase of dystrophin from baseline	Intra Subject CV			
	20%	25%	30%	35%
0.04%	19	29	41	55
0.06%	10	15	21	28
0.08%	7	10	13	18

**Abbreviations:** CV, coefficients of variability

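### SAP 7.1.1 does not fix the row structure of the primary model, and its sample code omits SUBJECT=, so it gives no p-value as written and the possible repairs are not equivalent

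*SAP*

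**What the plan says.** SAP 7 has cores taken from each muscle location and says that "multiple samples will be prepared from each muscle cores". SAP 7.1.1 then makes four statements that bear on the analysis row:

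- Summaries: "Within each muscle location, the best, median, and the average of the dystrophin levels" are to be described for each subject.
- Primary quantity: "The best dystrophin levels across all muscles are considered the primary analysis".
- Model: a repeated-measures mixed model on the log scale, "with factors of muscle locations, visits (baseline and Week 40) as fixed effects, and subjects as a random effect".
- Covariance: unstructured, and "if the model fails to converge, then a compound symmetry matrix will be used".

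The sample SAS code has visit and muscle location as fixed effects, a RANDOM statement for subject, and "repeated visit / type = un". Neither the RANDOM nor the REPEATED statement carries a SUBJECT= option.

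Protocol 8.4.2 has a simpler model: the log-transformed endpoint is "analyzed in a mixed model of repeated measures with week/treatment as a fixed effect and subject as a random effect", with no muscle term. SAP 10 lists the changes from the protocol, and the added muscle term is not among them.

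**The concern.** There are two linked faults.

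First, the analysis row is not defined. A best level taken across all muscles is one number per child per visit. A fixed effect for muscle location needs a location on every row, which suggests one row per muscle. With only one best row per visit, location could only be the label of the muscle that supplied the maximum. That is a covariate determined by the outcome, and the SAP does not describe it. The reduction from samples to cores to muscles to the analysed value is also not given.

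Second, a REPEATED statement without SUBJECT= treats the whole data set as one block. Every two rows from the same visit are then perfectly correlated in the residual matrix, whichever child they come from, and the model cannot be fitted. The stated fallback does not help.

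Someone must therefore repair the code, and the SAP does not say how. In an open-label single-arm study the choice could be made with data in hand, between a repair that holds its error rate and one that may not. The average, median, per-protocol, COVID-19 and immunohistochemistry analyses (SAP 7.1.3, 7.2.1 and 7.2.2) reuse the same model.

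**Working it through.** **Inputs from the documents.** N = 15 to 20; baseline 0.2% of control; increases of 0.04, 0.06 and 0.08 percentage points; intra-subject CV 20% to 35%; one-sided 5%; power 85% (SAP 3.3). Two muscles per biopsy visit (Protocol 3.1.1). Error rates are also shown at 2.5%, because SAP 10 gives a different level, printed as 0.025% and read here as 2.5%; that conflict is a separate matter.

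**Inputs assumed.** Complete data. The correlation rho between the two muscles' log changes within a child is not given, so a range is used. The simulations also assume log-scale variances.

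**1. Reproduce SAP Table 1.** The SAP states that "if the increase from baseline is 0.08% and the intra-subject coefficient is 30%, 13 evaluable subjects would be required". Take a paired t-test on one log difference per subject, with effect ln(1 + increase/0.2) and SD = sqrt(2) × CV. For the example:

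- effect = ln(1.4) = 0.3365; SD = 1.4142 × 0.30 = 0.4243
- n = 13: noncentrality 0.3365/0.4243 × sqrt(13) = 2.859, critical t(12) = 1.782, power 85.3%
- n = 12: power 82.3%

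So 13 is reproduced. Across the table 11 of 12 cells match exactly; the other (0.06%, CV 35%) gives 27 against 28. The sample size therefore rests on one value per subject per visit.

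**2. Rank of the covariance matrix.** Let R be the residual matrix and V = R + the random-intercept part. Without SUBJECT=, R has rank 2, because it depends only on the visit of each row. The intercept part has rank N. The subject and visit indicators share one dimension, so V has rank N + 2 − 1 = N + 1. A valid fit needs full rank.

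| Rows per visit | SUBJECT= | Rank of V, N=15 | Rank of V, N=20 |
|---|---|---|---|
| 1 (best) | none | 16 of 30 | 21 of 40 |
| 2 (per muscle) | none | 16 of 60 | 21 of 80 |
| 1 (best) | subjid | 30 of 30 | 40 of 40 |
| 2 (per muscle) | subjid | 30 of 60 | 40 of 80 |
| 2 (per muscle) | subjid*mlocation | 60 of 60 | 80 of 80 |

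The ranks are the same under unstructured and compound symmetry.

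**3. Error rate of the repairs that run.**

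*One best row, SUBJECT=subjid.* Simulation under no change (40,000 replicates; log-scale SDs: subject 0.4, subject-by-muscle 0.2, within-visit 0.2) gives one-sided error 4.9–5.1% at nominal 5% and 2.4–2.6% at 2.5%. The empirical SD is 1.01–1.02 times the model SE. If the location label is kept, it switches between visits in 27–33% of children. At rho = 0.33 it moves the visit estimate by about 0.15–0.17 SE, with no visible change in error rate.

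*Muscle rows, SUBJECT=subjid*mlocation.* Write v for the variance of one muscle's log change. The model takes the mean of 2N changes as having variance v/(2N), but its true variance is v(1 + rho)/(2N). The SE is too small by sqrt(1 + rho), and the true size is 1 − Φ(z/sqrt(1 + rho)), with z the critical value at the nominal level.

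| rho | sqrt(1+rho) | Size at 5% | Size at 2.5% |
|---|---|---|---|
| 0 | 1.000 | 5.0% | 2.5% |
| 0.33 | 1.153 | 7.7% | 4.5% |
| 0.5 | 1.225 | 9.0% | 5.5% |

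Example: 1.645/1.225 = 1.343, and 1 − Φ(1.343) = 0.090. Full REML fits (1,500 replicates, Monte Carlo error about 0.6–0.7 points) gave 4.3–5.0%, 6.3–6.9% and 9.0–9.1% at nominal 5%, with empirical SD over model SE of 0.99, 1.14–1.15 and 1.24–1.26.

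**4. Does the choice matter to the result?** At N = 20, a true ratio of 1.2, CV 30% and one-sided 5%, with rho from 0 to 0.8, power is 0.70 to 0.61 with one best row and 0.86 to 0.80 with muscle rows. The two repairs reach opposite significance decisions in about 19–20% of simulated trials.

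**The case against.** The wording leans towards one best value per subject per visit. SAP 7.1.1 contrasts values across all muscles with those within each location. It introduces the within-location values as descriptive summaries and later treats them as subgroup analyses. Table 1 fits the same reading. Text and code both name the subject as the unit, so SUBJECT=subjid is the natural completion, and with one best row it holds its error rate. The inflated rates belong to a SUBJECT= specification that the SAP never mentions and to a correlation that it does not give. The code is labelled a sample, its failure would show at the first run, and a dry run on dummy data could expose it before results are known.

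Most of this stands. It limits the harm: no silently wrong p-value can come from the code as written, and the inflation is conditional. It does not remove the fault. The muscle-location factor is in the model sentence as well as in the sample code, so correcting the syntax alone does not settle the row. The compound-symmetry fallback is a stated rule, and it fails too. With muscle rows, the natural completion remains singular, which would push a programmer towards the repair that can inflate error.

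**Conclusion.** The point holds and should be fixed. As written, neither the primary code nor its fallback gives a valid standard error or p-value, for either row layout. That rests on matrix algebra and on PROC MIXED treating the data as one block when SUBJECT= is absent; SAS itself was not run.

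On the better-supported reading, one best row with SUBJECT=subjid, there is no material error-rate problem. The random intercept is then redundant but harmless. The inflation to 7.7% or 9.0% applies only if muscle rows are fitted with SUBJECT=subjid*mlocation and rho is 0.33 or 0.5; at rho = 0 there is none. The power and disagreement figures depend on assumed variances and effects, but the ranks do not. The unlisted departure from the Protocol 8.4.2 model is a documentation gap alongside this.

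**What to change.** In SAP 7.1.1:

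- State that the primary analysis uses one log value per subject per visit, and how it is derived from samples, cores and muscles.
- Fit visit as the only fixed effect, with `repeated visit / subject=subjid type=un`, no RANDOM statement and no location term.
- Name the degrees-of-freedom method, for example Kenward-Roger.

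For complete pairs this is the paired comparison behind Table 1, and it agrees with Protocol 8.4.2 in having no muscle term.

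If muscle-level rows are intended instead, keep location and include random subject, subject-by-visit and subject-by-location effects, so that correlation between the two muscles' changes is modelled.

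Carry the same correction into the average, median, per-protocol, COVID-19 and immunohistochemistry analyses. List any model that still differs from Protocol 8.4.2 in SAP 10.

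The cost is wording and code; no new data are needed. The interval may be slightly wider than one that treats the two muscles as independent.

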### 3.1.1 Muscle biopsy samples

Biopsies will be performed before initiation of ataluren therapy and after 40 weeks of treatment by appropriately trained staff at [REDACTED]. All subjects will have a physical exam and a history taken and recorded within 7 days of the procedure, usually on the day before the procedure to assess biopsy locations and determine if there is any intercurrent illness that places a subject at higher risk.

Biopsy of the [REDACTED] and [REDACTED] muscles will be performed using an established core biopsy procedure (Gallo 2018). If the [REDACTED] muscle is considered by the investigator to be too small for a biopsy sample (or the obtained sample is considered not evaluable for analysis), the [REDACTED] muscle may be used. Up to approximately 450 mg of muscle tissue (up to [REDACTED] cores per muscle) will be taken from each muscle at both Visit 1 and Visit 3. Conscious sedation will be offered with propofol and fentanyl to provide sedation and analgesia by physicians credentialed to monitor and provide sedation in an outpatient setting. Following sedation, vital signs will be monitored until the subject returns to pre-sedation baseline values. These techniques are standard of care at [REDACTED] for minor procedures on young patients.

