### 3.2 Scientific Rationale for Study Design

The study is designed to generate additional data on the effect of ataluren on promoting the production of dystrophin protein in nmDMD subjects. It is known that small increases in dystrophin levels can result in milder disease phenotype in nmDMD patients. The levels of dystrophin in patients with Becker muscular dystrophy (BMD) have been reported to be higher than that observed in patients with DMD (Anthony 2014). Consequently, patients with BMD generally have less severe disease compared with those with DMD; BMD patients often show a later onset of disease and slower disease progression (Muntoni 2003, Aartsma-Rus 2006).

As described in Section 1.2.1, the ability of ataluren to promote ribosomal readthrough of premature stop codons has been demonstrated in a range of in vivo and in vitro preclinical assays. In addition, ataluren-associated increases in dystrophin protein levels was assessed in a prior clinical study. Of patients treated with ataluren 10, 10, 20 mg/kg, 55% (8/20) had an increase in dystrophin expression post-ataluren treatment (Finkel 2013). The findings from this study were consistent with ataluren treatment increasing dystrophin level and indicated that the protein correctly localized to the muscle cell membranes, suggesting functional activity (Finkel 2013).

Assessing dystrophin levels in patients with nmDMD can be challenging due to inherent difficulty in obtaining muscle samples that contain sufficient amounts of intact muscle cells for analysis, as nmDMD muscle, particularly in older patients, are often heterogenous with respect to fibrofatty replacement of muscle.

From prior clinical trial experience, it is anticipated that although levels of dystrophin may increase in nmDMD muscle from baseline following ataluren therapy, the amount of dystrophin will still be low; hence, sensitive assays with good specificity are necessary to evaluate change in dystrophin levels with treatment.

Method of biopsy sampling can also impact results. For example, variability can be introduced by assessing a bilateral muscle sampled from one side of the body before treatment and from the other side after treatment.

This current study is designed to mitigate some of these difficulties.

- Biopsies will be collected from subjects  $\geq 2$  and  $< 8$  years of age who are symptomatic to increase the chance of collecting less heterogenous muscle tissue.

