- Up to approximately 450 mg of muscle tissue (up to █ cores per muscle) will be collected from the █ muscles located on the █ side of the body before initiation of ataluren therapy and after 40 weeks of treatment. If the █ muscle is considered by the investigator to be too small for biopsy sampling (or the obtained sample is considered not evaluable for analysis), the █ muscle may be used.
- The same muscles will be sampled pre- and post-40 weeks of ataluren therapy.

- Two validated, highly sensitive assays will be used to measure ataluren-associated increases in dystrophin levels and to evaluate whether the protein localizes correctly to the muscle membrane.

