## 7.2. Secondary Efficacy Analyses

### 7.2.1. Secondary Efficacy Analysis

The secondary efficacy endpoint is the percent change from baseline in dystrophin levels (mean membrane stain density) after 40 weeks of ataluren therapy as determined by a validated IHC assay. Within each muscle location, the best, median, and the average dystrophin levels of the muscle cores will be summarized using descriptive statistics for each subject. The secondary efficacy endpoint will be analyzed using the same method as described in Section 7.1.1 (Primary Analysis). The best dystrophin levels across all muscles are considered the primary interest. As supportive analyses, the average and median dystrophin levels across all muscles, and subgroup analyses of the best, median, and mean dystrophin levels within each muscle location will be considered. In addition to dystrophin levels (the mean staining intensity), the percentage of positive fibers will also be summarized using descriptive statistics.

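### The primary dystrophin summary is a maximum, and no readable rule matches the number of evaluable cores or samples between baseline and Week 40

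*SAP*

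**What the plan says.** SAP 7.1.1, on ECL: "The best dystrophin levels across all muscles are considered the primary analysis". SAP 7.2.1, on immunohistochemistry: "The best dystrophin levels across all muscles are considered the primary interest". Neither section defines *best*.

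The unit is described in two ways. SAP 7 says that "multiple samples will be prepared from each muscle cores" and that "Dystrophin levels will be measured from each sample by both ECL and IHC". The descriptive summary in 7.1.1 covers "the best, median, and the average of the dystrophin levels and the corresponding % normal values of the muscle cores" within each muscle location. No step says how several samples become one core value. The phrase *across all muscles* can mean one value per subject and visit, while the sample SAS code carries a muscle-location term, which points to one value per location.

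On quantity, Protocol 3.1.1 sets a ceiling for each muscle at both visits: "Up to approximately 450 mg of muscle tissue". It also allows another muscle to be used when a sample is not evaluable. The number of cores is redacted in both documents. Protocol 3.2 warns of "inherent difficulty in obtaining muscle samples that contain sufficient amounts of intact muscle cells for analysis" and gives one matching rule: "The same muscles will be sampled pre- and post-40 weeks of ataluren therapy". Protocol 6.3 has both visits' samples assayed at the same time by staff blinded to visit.

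The average and median are planned as supportive and sensitivity analyses (SAP 7.1.1, 7.1.3, 7.2.1, 7.2.2).

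**The concern.** The expected maximum of several measurements grows with their number, even when nothing biological has changed. Sampling the same muscles under the same tissue ceiling does not guarantee the same number of evaluable cores or samples. Blinding and simultaneous assay deal with reader and batch effects, not with counts.

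The trial has no control arm. If Week 40 systematically yielded more evaluable units than baseline, the primary analysis would show a rise that could not be separated from a drug effect. If it yielded fewer, a real rise could be hidden. Because the sample-to-core step and the number of records per subject are not stated, two programmers could also derive different primary datasets from the same assay results.

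**Working it through.** **The plan's own figure first.** Protocol Table 6 and SAP Table 1 give 13 evaluable subjects for a rise of 0.08 on a baseline of 0.2, with CV 30%, one-sided 5% and power 85%. A paired t-test on the log scale has difference ln(0.28/0.20) = 0.336 and SD √2 × 0.30 = 0.424. With n = 13 the noncentrality is 0.336/0.424 × √13 = 2.86 and the power is 0.853. The figure reproduces, so the sample-size table is not in question. The smallest planned effect is 0.04/0.2 = +20%.

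**Inputs for the check.** From the documents: one-sided 5% (SAP 7.1.1) and 15 to 20 subjects planned. Assumed: n = 18, unit log SD 0.30, visit-level log SD 0.20, independent units, all unit counts, and no drug effect. SAP Section 10 prints a stricter one-sided level, 0.025%. Results at 2.5% are also shown, as an assumed reading of that figure; the two sections need reconciling separately.

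**Shift.** The expected maximum of k standard normal values is 1.029 for k = 4, 1.163 for k = 5 and 1.267 for k = 6. The log shift is the difference in these values × 0.30.
- 4 v 5: (1.163 − 1.029) × 0.30 = 0.040, or +4.1%
- 4 v 6: (1.267 − 1.029) × 0.30 = 0.071, or +7.4%
- 6 v 4: −0.071, or −6.9%

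**False-positive rate.** Simulation, 40,000 replicates per case, paired t-test on the log change in the per-subject maximum. This simplifies the planned MMRM.

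| Units, baseline v Week 40 | Shift | Rejection at 5% | Rejection at 2.5% | Equal-count version, at 5% |
|---|---|---|---|---|
| 4 v 4 | 0% | 5% | 2.5% | 5% |
| random 3–8 at both visits | 0% | 5% | – | – |
| 4 v 5 | +4% | 10–11% | about 6% | about 5% |
| 4 v 6 | +7% | 17–18% | 10–11% | about 5% |
| 6 v 4 | −7% | about 1% | 0.4% | about 5% |

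**Sensitivity of 4 v 6, at 5%.**
- Unit SD 0.15 to 0.40: +3.6% to +10%, rejection 12–21%.
- Visit SD 0.10 to 0.30: 23% down to 14%. With no visit-level variation: 26–27%.
- n from 15 to 20: 16–19%.
- Imbalance in only one third of subjects: +2.4% and 8%. In half: +3.6% and 10%.

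**Other readings of the unit.**
- One maximum per location, two muscles, 2 v 3 units each: (0.846 − 0.564) × 0.30 = 0.085, or +8.8%, with 24% rejection. Equal-count version: 5%.
- Maximum of core means (2 samples per core, within-core correlation 0 to 0.8), 4 v 5 cores: +2.9% to +3.9% and 9.5–10.6%.
- Maximum of core means, 4 cores at both visits but 2 v 3 samples in each: −3.2% to −0.4% and 2–5%. On this reading only extra cores inflate the result.

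**Equal-count step.** For k values at the larger visit and m at the smaller, sort the k log values and weight the i-th smallest by C(i−1, m−1)/C(k, m). For k = 6 and m = 4 the weights on the three largest are 1/15, 4/15 and 10/15. This is the mean log maximum over all subsets of size m, so both visits have the same expectation when nothing has changed.

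**The case against.** The case against has several sound parts. The core count is redacted, and the readable SAP text on cores carries no ceiling wording; that is in the protocol. A fixed, equal number of cores may well be specified, and what is hidden is not missing. This stands. What remains is narrower: a fixed number taken does not fix the number evaluable, and samples per core are left open.

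The definition gap is modest. Beside median and average, and with an alternative of an increase, highest is the only sensible reading of *best*. The muscle-location term, together with the contrast in 7.1.1 between results across muscles and within a location, favours one value per location. Only the sample-to-core step is wholly unstated.

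The average and median are prespecified. In simulation the mean log value holds its level under 4 v 6 (4.8% at a nominal 5%), so a count artefact should appear as disagreement between the summaries. That helps reveal the problem but does not settle the primary test.

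Protocol 3.2 also gives a reason to favour the best tissue, since dystrophic muscle is patchy. Nothing here requires abandoning the maximum.

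A reader might infer that Week 40 biopsies did yield more units, or that the amendment which changed the biopsy amount produced such a difference. The documents support neither. They give no counts and no enrolment dates, and the earlier biopsy amount is redacted.

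**Conclusion.** The concern holds as a conditional weakness, not as a demonstrated bias. The leading summary for both assays depends on how many evaluable units each visit supplies, and no readable rule makes those numbers equal. Equal or randomly varying counts do no harm. A systematic excess of one or two units at Week 40, on a base of four, would give an apparent rise of about 4% or 7% and raise a nominal 5% error to about 10–11% or 17–18%. A deficit would bias the other way.

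These rates rest on assumed SDs, counts and independence, and on a paired t-test in place of the MMRM. They are lower at 2.5% and higher without visit-level variation. Every count shift computed is below the smallest planned effect of +20%, so a count artefact of this size could not by itself stand in for the planned effect. A reader might infer that a significant primary result would be untrustworthy; the documents do not support that. This is a cheap improvement worth making, with medium confidence in its practical importance.

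**What to change.** In SAP 7.1.1 and 7.2.1:
- State that *best* is the maximum, how sample values are combined into a core value, and whether the model takes one value per location or one per subject.
- Compute the best level on an equal number of evaluable units per muscle at both visits within a subject, for example as the mean log maximum over all subsets of the smaller visit's size. If the unit is the single sample, equalise cores and samples per core.
- Tabulate evaluable cores and samples by subject, muscle and visit.
- Keep the average and median as the planned supportive analyses.

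The cost is a few sentences, one derivation step and one table, with no new data. Some samples at the visit with more units are not fully used, and the step changes nothing if counts are already equal. It does not protect against a change in between-sample spread: at 4 v 4, a unit SD rising from 0.30 to 0.40 gives +7% and 15% rejection with the arithmetic mean held, or +11% and 24% with the log mean held.
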